7.8 Trial Blinding/Masking

This is an open-label trial; therefore, the Sponsor, investigator and subject will know the treatment administered.

7.9 Concomitant Medications/Vaccinations (allowed & prohibited)

Medications or vaccinations specifically prohibited in the exclusion criteria are not allowed during the ongoing trial. If there is a clinical indication for one of these or other medications or vaccinations specifically prohibited during the trial, discontinuation from trial therapy or vaccination may be required. The investigator should discuss any questions regarding this with the Merck Clinical team. The final decision on any supportive therapy or vaccination rests with the investigator and/or the subject's primary physician.

7.9.1 Acceptable Concomitant Medications

All treatments that the investigator considers necessary for a subject's welfare may be administered at the discretion of the investigator in keeping with the community standards of medical care. All concomitant medication will be recorded on the case report form (CRF) including all prescription, over-the-counter (OTC), herbal supplements, and IV medications and fluids. If changes occur during the trial period, documentation of drug dosage, frequency, route, and date may also be included on the CRF.

All concomitant medications received within 28 days before the first dose of trial treatment and 30 days after the last dose of trial treatment should be recorded. Concomitant medications administered after 30 days after the last dose of trial treatment should be recorded for SAEs and ECIs.

Use of growth factors, including filgrastim or pegfilgrastim and erythropoietin, is permitted per institutional policy and in accordance with American Society of Clinical Oncology (ASCO) guidelines.¹³⁸ Red blood cell transfusions are permitted per institutional guidelines. Platelet transfusions are permitted, but will be considered a DLT if required during the DLT period.

7.9.2 Prohibited Concomitant Medications

Subjects are prohibited from receiving the following therapies during the Screening and Treatment Phase of this trial:

- Antineoplastic systemic chemotherapy or biological therapy
- Immunotherapy not specified in this protocol
- Chemotherapy not specified in this protocol
- Investigational agents other than those specified in this protocol
- Radiation therapy
- Live vaccines within 30 days prior to the first dose of trial treatment and while participating in the trial. Examples of live vaccines include, but are not limited to, the following: measles, mumps, rubella, varicella/zoster, yellow fever, rabies, BCG, and typhoid vaccine.
- Systemic glucocorticoids for any purpose other than to modulate symptoms from an event of clinical interest or suspected immunologic etiology. The use of physiologic doses of corticosteroids may be approved after consultation with the Sponsor.
- Other histone deacetylase inhibitors (e.g. valproic acid).

Subjects who, in the assessment by the investigator, require the use of any of the aforementioned treatments for clinical management should be removed from the trial. Subjects may receive other medications that the investigator deems to be medically necessary.

The Exclusion Criteria describes other medications that are prohibited in this trial.

There are no prohibited therapies during the Post-Treatment Follow-up Phase.

7.10 Rescue Medications & Supportive Care

7.10.1 Supportive Care Guidelines

Subjects should receive appropriate supportive care measures as deemed necessary by the treating investigator. Use of growth factors, including filgrastim or pegfilgrastim and erythropoietin, is permitted per institutional policy and in accordance with American Society of Clinical Oncology (ASCO) guidelines.¹³⁸ Red blood cell transfusions are permitted per institutional guidelines. Platelet transfusions are permitted, but will be considered a DLT if required during the DLT period.

Suggested supportive care measures for the management of adverse events with potential immunologic etiology are outlined below and in the ECI guidance document. Where appropriate, these guidelines include the use of oral or intravenous treatment with corticosteroids as well as additional anti-inflammatory agents if symptoms do not improve with administration of corticosteroids. Note that several courses of steroid tapering may be necessary as symptoms may worsen when the steroid dose is decreased. For each disorder, attempts should be made to rule out other causes such as metastatic disease or bacterial or viral infection, which might require additional supportive care. The treatment guidelines are intended to be applied when the investigator determines the events to be related to pembrolizumab.

Note: if after the evaluation the event is determined not to be related, the investigator does not need to follow the treatment guidance (as outlined below). Refer to Section 7.6.1 for dose modification.

It may be necessary to perform conditional procedures such as bronchoscopy, endoscopy, or skin photography as part of evaluation of the event.

Please review the ECI document in detail for management of IrAEs and corticosteroid dosing, the below is meant to be a quick reference.

- **Myocarditis**
 - For suspected immune-mediated myocarditis, ensure adequate evaluation to exclude other etiologies.
 - Administer corticosteroids as appropriate.
- **Pneumonitis:**
 - For **Grade 2 events**, treat with systemic corticosteroids. When symptoms improve to Grade 1 or less, steroid taper should be started and continued over no less than 4 weeks.
 - For **Grade 3-4 events**, immediately treat with intravenous steroids. Administer additional anti-inflammatory measures, as needed.

- Add prophylactic antibiotics for opportunistic infections in the case of prolonged steroid administration.
- **Diarrhea/Colitis:**
Subjects should be carefully monitored for signs and symptoms of enterocolitis (such as diarrhea, abdominal pain, blood or mucus in stool, with or without fever) and of bowel perforation (such as peritoneal signs and ileus).
 - All subjects who experience diarrhea/colitis should be advised to drink liberal quantities of clear fluids. If sufficient oral fluid intake is not feasible, fluid and electrolytes should be substituted via IV infusion. Supportive care with loperamide or other standard anti-diarrheal medication is acceptable. For Grade 2 or higher diarrhea, consider GI consultation and endoscopy to confirm or rule out colitis.
 - For **Grade 2 diarrhea/colitis**, administer oral corticosteroids.
 - For **Grade 3 or 4 diarrhea/colitis**, treat with intravenous steroids followed by high dose oral steroids.
 - When symptoms improve to Grade 1 or less, steroid taper should be started and continued over no less than 4 weeks.
- **Type 1 diabetes mellitus (if new onset, including diabetic ketoacidosis [DKA]) or \geq Grade 3 Hyperglycemia, if associated with ketosis (ketonuria) or metabolic acidosis (DKA)**
 - For **T1DM** or **Grade 3-4** Hyperglycemia
 - Insulin replacement therapy is recommended for Type I diabetes mellitus and for Grade 3-4 hyperglycemia associated with metabolic acidosis or ketonuria.
 - Evaluate patients with serum glucose and a metabolic panel, urine ketones, glycosylated hemoglobin, and C-peptide.
- **Hypophysitis:**
 - For **Grade 2** events, treat with corticosteroids. When symptoms improve to Grade 1 or less, steroid taper should be started and continued over no less than 4 weeks. Replacement of appropriate hormones may be required as the steroid dose is tapered.
 - For **Grade 3-4** events, treat with an initial dose of IV corticosteroids followed by oral corticosteroids. When symptoms improve to Grade 1 or less, steroid taper should be started and continued over no less than 4 weeks. Replacement of appropriate hormones may be required as the steroid dose is tapered.
- **Hyperthyroidism or Hypothyroidism:**

Thyroid disorders can occur at any time during treatment. Monitor patients for changes in thyroid function (at the start of treatment, periodically during treatment, and as indicated based on clinical evaluation) and for clinical signs and symptoms of thyroid disorders.

- **Grade 2** hyperthyroidism events (and **Grade 2-4** hypothyroidism):
 - In hyperthyroidism, non-selective beta-blockers (e.g. propranolol) are suggested as initial therapy.
 - In hypothyroidism, thyroid hormone replacement therapy, with levothyroxine or liothyroinine, is indicated per standard of care.
- **Grade 3-4** hyperthyroidism
 - Treat with an initial dose of IV corticosteroid followed by oral corticosteroids. When symptoms improve to Grade 1 or less, steroid taper should be started and continued over no less than 4 weeks. Replacement of appropriate hormones may be required as the steroid dose is tapered.
- **Hepatic:**
 - For **Grade 2** events, monitor liver function tests more frequently until returned to baseline values (consider weekly).
 - Treat with IV or oral corticosteroids
 - For **Grade 3-4** events, treat with intravenous corticosteroids for 24 to 48 hours.
 - When symptoms improve to Grade 1 or less, a steroid taper should be started and continued over no less than 4 weeks.
- **Renal Failure or Nephritis:**
 - For **Grade 2** events, treat with corticosteroids.
 - For **Grade 3-4** events, treat with systemic corticosteroids.
 - When symptoms improve to Grade 1 or less, steroid taper should be started and continued over no less than 4 weeks.
- **Management of Infusion Reactions:** Pembrolizumab may cause severe or life threatening infusion-reactions including severe hypersensitivity or anaphylaxis. Signs and symptoms usually develop during or shortly after drug infusion and generally resolve completely within 24 hours of completion of infusion.

Table 8 below shows treatment guidelines for subjects who experience an infusion reaction associated with administration of pembrolizumab (MK-3475).

Table 8. Pembrolizumab Infusion Reaction Treatment Guidelines

NCI CTCAE Grade	Treatment	Premedication at Subsequent Dosing
Grade 1 Mild reaction; infusion interruption not indicated; intervention not indicated	Increase monitoring of vital signs as medically indicated until the participant is deemed medically stable in the opinion of the investigator.	None
Grade 2 Requires therapy or infusion interruption but responds promptly to symptomatic treatment (e.g., antihistamines, NSAIDs, narcotics, IV fluids); prophylactic medications indicated for ≤ 24 hrs	
Stop Infusion.
 
Additional appropriate medical therapy may include but is not limited to:
 
IV fluids Antihistamines NSAIDs Acetaminophen Narcotics
 
Increase monitoring of vital signs as medically indicated until the participant is deemed medically stable in the opinion of the investigator.
 
If symptoms resolve within 1 hour of stopping drug infusion, the infusion may be restarted at 50% of the original infusion rate (e.g. from 100 mL/hr to 50 mL/hr). Otherwise dosing will be held until symptoms resolve and the participant should be premedicated for the next scheduled dose.
 
Participants who develop Grade 2 toxicity despite adequate premedication should be permanently discontinued from further study drug treatment
	
Participant may be premedicated 1.5h (± 30 minutes) prior to infusion of pembrolizumab with:
 
Diphenhydramine 50 mg po (or equivalent dose of antihistamine).
 
Acetaminophen 500-1000 mg po (or equivalent dose of analgesic).

Grades 3 or 4 Grade 3: Prolonged (i.e., not rapidly responsive to symptomatic medication and/or brief interruption of infusion); recurrence of symptoms following initial improvement; hospitalization indicated for other clinical sequelae (e.g., renal impairment, pulmonary infiltrates) Grade 4: Life-threatening; pressor or ventilatory support indicated	
Stop Infusion.
 
Additional appropriate medical therapy may include but is not limited to:
 
Epinephrine** IV fluids Antihistamines NSAIDs Acetaminophen Narcotics Oxygen Pressors Corticosteroids
 
Increase monitoring of vital signs as medically indicated until the participant is deemed medically stable in the opinion of the investigator.
 
Hospitalization may be indicated.
 
**In cases of anaphylaxis, epinephrine should be used immediately.
 
Participant is permanently discontinued from further study drug treatment.
	No subsequent dosing

Appropriate resuscitation equipment should be available at the bedside and a physician readily available during the period of drug administration. For further information, please refer to the Common Terminology Criteria for Adverse Events v4.0 (CTCAE) at <http://ctep.cancer.gov>

7.11 Diet/Activity/Other Considerations

7.11.1 Diet

Subjects should maintain a normal diet unless modifications are required to manage an AE such as diarrhea, nausea or vomiting.

7.11.2 Contraception

Study treatment may have adverse effects on a fetus in utero. Furthermore, it is not known if study treatment has transient adverse effects on the composition of sperm.

For this trial, male subjects will be considered to be of non-reproductive potential if they have azoospermia (whether due to having had a vasectomy or due to an underlying medical condition).

Female subjects will be considered of non-reproductive potential if they are either:

- (1) postmenopausal (defined as at least 12 months with no menses without an alternative medical cause; in women <45 years of age a high follicle stimulating hormone (FSH) level in the postmenopausal range may be used to confirm a post-menopausal state in women not using hormonal contraception or hormonal replacement therapy. In the absence of 12 months of amenorrhea, a single FSH measurement is insufficient.);

OR

- (2) have had a hysterectomy and/or bilateral oophorectomy, bilateral salpingectomy or bilateral tubal ligation/occlusion, at least 6 weeks prior to screening;

OR

- (3) has a congenital or acquired condition that prevents childbearing.

Female and male subjects of reproductive potential must agree to avoid becoming pregnant or impregnating a partner, respectively, while receiving study drug and for 120 days after the last dose of study drug by complying with one of the following:

- (1) practice abstinence[†] from heterosexual activity;

OR

- (2) use (or have their partner use) acceptable contraception during heterosexual activity.

Acceptable methods of contraception are[‡]:

Single method (one of the following is acceptable):

- intrauterine device (IUD)
- vasectomy of a female subject's male partner
- contraceptive rod implanted into the skin

Combination method (requires use of two of the following):

- diaphragm with spermicide (cannot be used in conjunction with cervical cap/spermicide)
- cervical cap with spermicide (nulliparous women only)
- contraceptive sponge (nulliparous women only)
- male condom or female condom (cannot be used together)
- hormonal contraceptive: oral contraceptive pill (estrogen/progestin pill or progestin-only pill), contraceptive skin patch, vaginal contraceptive ring, or subcutaneous contraceptive injection

†Abstinence (relative to heterosexual activity) can be used as the sole method of contraception if it is consistently employed as the subject's preferred and usual lifestyle and if considered acceptable by local regulatory agencies and ERCs/IRBs. Periodic abstinence (e.g., calendar, ovulation, sympto-thermal, post-ovulation methods, etc.) and withdrawal are not acceptable methods of contraception.

‡If a contraceptive method listed above is restricted by local regulations/guidelines, then it does not qualify as an acceptable method of contraception for subjects participating at sites in this country/region.

Subjects should be informed that taking the study medication may involve unknown risks to the fetus (unborn baby) if pregnancy were to occur during the study. In order to participate in the study subjects of childbearing potential must adhere to the contraception requirement (described above) from the day of study medication initiation (or 14 days prior to the initiation of study medication for oral contraception) throughout the study period up to 120 days after the last dose of trial therapy. If there is any question that a subject of childbearing potential will not reliably comply with the requirements for contraception, that subject should not be entered into the study.

7.11.3 Use in Pregnancy

If a subject inadvertently becomes pregnant while on study treatment, the subject will immediately be removed from the study. The site will contact the subject at least monthly and document the subject's status until the pregnancy has been completed or terminated. The outcome of the pregnancy will be reported to the Sponsor and to Merck without delay and within 24 hours to the Sponsor and within 2 working days to Merck if the outcome is a serious adverse experience (e.g., death, abortion, congenital anomaly, or other disabling or life-threatening complication to the mother or newborn).

The study investigator will make every effort to obtain permission to follow the outcome of the pregnancy and report the condition of the fetus or newborn to the Sponsor. If a male subject impregnates his female partner the study personnel at the site must be informed immediately and the pregnancy reported to the Sponsor and to Merck and followed as described above and in Section 14.2.2.

7.11.4 Use in Nursing Women

It is unknown whether study treatment (pembrolizumab or vorinostat) is excreted in human milk. Since many drugs are excreted in human milk, and because of the potential for serious adverse reactions in the nursing infant, subjects who are breast-feeding are not eligible for enrollment.

7.12 Subject Withdrawal/Discontinuation Criteria

Subjects may withdraw consent at any time for any reason or be dropped from the trial at the discretion of the investigator should any untoward effect occur. In addition, a subject may be withdrawn by the investigator or the Sponsor if enrollment into the trial is inappropriate, the trial plan is violated, or for administrative and/or other safety reasons. Specific details regarding discontinuation or withdrawal are provided in Section 9.5.2 - Other Procedures.

A subject must be discontinued from the trial for any of the following reasons:

- The subject or legal representative (such as a parent or legal guardian) withdraws consent.
- Confirmed radiographic disease progression

Note: A subject may be granted an exception to continue on treatment with confirmed radiographic progression if clinically stable or clinically improved, please see Section 9.5.3.5

- Unacceptable adverse experiences, either DLT (Section 7.2) or other unacceptable toxicity (Section 10.2).
- Intercurrent illness that prevents further administration of treatment

- Investigator's decision to withdraw the subject
- The subject has a confirmed positive serum pregnancy test
- Noncompliance with trial treatment or procedure requirements
- The subject is lost to follow-up
- Completed 24 months of uninterrupted treatment with pembrolizumab or 35 administrations of study pembrolizumab, whichever is later.

Note: 24 months of study medication is calculated from the date of first dose.

- Administrative reasons

The End of Treatment and Follow-up visit procedures are listed in Section 8 (Protocol Flow Chart) and Section 9.5.3 (Visit Requirements). After the end of treatment, each subject will be followed for 30 days for adverse event monitoring (serious adverse events will be collected for 90 days after the end of treatment). Subjects who discontinue for reasons other than progressive disease will have post-treatment follow-up for disease status until disease progression, initiating a non-study cancer treatment, withdrawing consent or becoming lost to follow-up. After documented disease progression each subject will be followed for overall survival until death, withdrawal of consent, or the end of the study (last patient off therapy), whichever occurs first.

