7.1.1 Treatment Duration

Study treatment will continue until the subject completes 24 months of treatment with the study regimen, or experiences radiographically-confirmed PD (Section 9.2.6 and Section 9.2.6.1), unacceptable adverse experiences, either DLT (Section 7.2) or other unacceptable toxicity (section 10.2), or meets other criteria for study withdrawal or treatment discontinuation

7.1.2 Rules for Phase I Dose Escalation, De-Escalation and Expansion: Adapted Rolling 6 Design

This phase I trial will employ a modified Rolling 6 design, a more conservative version of the Rolling 6 design of Skolnik, et al²⁹. In this design, at most, 3 patients will be under observation for DLT on the current test dose level at any time. Patients who are not evaluable for DLT will be replaced. Once each patient is evaluable for toxicity and passes without a DLT, an additional patient *may* be accrued on that dose level – up to 6 patients. Once 3 patients are evaluable with no patient at that dose level experiencing a DLT, the dose can be escalated, or up to 3 additional patients may be treated at the current dose level. Although this design does not require that 6 patients be treated, no more than 6 evaluable patients will be accrued to any dose level during the dose finding portion of this study. If at any time, the dose level has 1 documented DLT with fewer than 6 evaluable patients, accrual will continue until 6 patients are evaluable. Escalation will terminate as soon as two or more patients experience any DLT attributable to the study treatment, at a given dose level. MTD will be declared at the highest dose level at which 6 patients have been treated and at most 1/6 patients experiences DLT. If more than 1/6 patients experiences DLT, then the next lower dose will be expanded. There will be no intrapatient dose escalation. These rules are outlined in Table 4:

Table 4. Dose Escalation Rules

# Patients on Current Level			Action
With DLT [^]	Evaluable	Evaluable + At Risk [^]	
0	0	1-2	Accrue next patient at this level*
0	0	3	Hold accrual
0	1	1-3	Accrue next patient at this level
0	1	4	Hold accrual
0	2	2-4	Accrue next patient at this level
0	2	5	Hold accrual
0	3-6	3-6	Accrue next patient at the next higher level* ^{+,+}
1	1	1-2	Accrue next patient at this level
1	1	3	Hold Accrual
1	2	2	Accrue next patient at this level
1	2	3-4	Hold accrual
1	3-5	3-5	Accrue next patient at this level
1	3-5	6	Hold accrual
1	6	6	Accrue next patient at the next higher level*

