7.6.1.2 Pembrolizumab Dose Modification (Escalation/Titration/Other)

Note: If pembrolizumab administration is held for toxicity, and the toxicity is most likely attributed to pembrolizumab and not attributed to vorinostat, administration of vorinostat can continue.

During the Phase I portion of the study, no intrapatient dose de-escalation will be allowed during the DLT period. After the DLT period, the following dose modifications are permitted for pembrolizumab-related adverse events according the guidelines outlined below in Table 5 for pembrolizumab. If, according to Table 5, pembrolizumab is discontinued permanently, the patient should continue to receive vorinostat.

Adverse events (both non-serious and serious) associated with pembrolizumab exposure may represent an immunologic etiology. These immune-related adverse events may occur shortly after the first dose or several months after the last dose of pembrolizumab treatment and may affect more than one body system simultaneously. Therefore, early recognition and initiation of treatment is critical to reduce complications. Based on existing clinical study data, most irAEs were reversible and could be managed with interruptions of pembrolizumab, administration of corticosteroids and/or other supportive care. For suspected irAEs, ensure adequate evaluation to confirm etiology or exclude other causes. Additional procedures or tests such as bronchoscopy, endoscopy, skin biopsy may be included as part of the evaluation. Based on the severity of irAEs, withhold or permanently discontinue pembrolizumab and administer corticosteroids. Dose modification and toxicity management guidelines for irAEs associated with pembrolizumab are provided in Table 5. See Section 7.10.1 for supportive care guidelines, including use of corticosteroids.

Table 5. Dose modification and toxicity management guidelines for immune-related AEs associated with pembrolizumab

General instructions:

1. Corticosteroid taper should be initiated upon AE improving to Grade 1 or less and continue to taper over at least 4 weeks.
2. For situations where pembrolizumab has been withheld, pembrolizumab can be resumed after AE has been reduced to Grade 1 or 0 and corticosteroid has been tapered. Pembrolizumab should be permanently discontinued if AE does not resolve within 12 weeks of last dose or corticosteroids cannot be reduced to ≤ 10 mg prednisone or equivalent per day within 12 weeks.

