7.7.1 Vorinostat Dose/Delay Modification Guidelines

Note: If vorinostat is dose-reduced or held for toxicity, and the toxicity is most likely attributed to vorinostat and not attributed to pembrolizumab, administration of pembrolizumab can continue.

Vorinostat dose reductions are NOT permitted during the DLT period. Following the completion of the DLT period, the vorinostat doses may be modified for toxicity according to the below guidelines in Tables 6 and 7. Vorinostat dose delays are permitted during the DLT period due to study treatment-related toxicity, however, if a patient misses > 30% of the vorinostat doses due to toxicity, this will be considered a DLT.

Table 6. Vorinostat Dose Reduction Guidelines

Vorinostat Dose Reductions				
Starting dose	1 st dose reduction	2 nd dose reduction	3 rd dose reduction	4 th dose reduction
Dose Level 1	Dose Level -1	Dose Level -2	Dose Level -2 schedule but 100mg daily	N/A**
Dose Level 2	Dose Level 1	Dose Level -1	Dose Level -2	Dose Level -2 schedule but 100mg daily

mg = milligrams; po = orally; BID = twice daily

**Patients requiring a dose reduction to below 100 mg daily of vorinostat at dose level -2 schedule will discontinue vorinostat permanently.

Table 7. Vorinostat Dose Delay Guidelines

Grade of Event	Management/Next Dose for Vorinostat
≤ Grade 1	No change in dose.

Grade 2	If tolerable to patient, no change needed but monitor patient more frequently. If intolerable to patient, hold* drug until toxicity \leq Grade 1 then resume drug at same dose.
Grade 3 (1 st occurrence)	Hold* until \leq Grade 1. Resume at same dose.
Grade 3 (after 1 st dose reduction)	Hold* until \leq Grade 1: if toxicity related to drug, resume at 1 dose lower; if toxicity not related to drug, resume at same dose or 1 dose lower.**
Grade 3 (subsequent occurrences)	Hold* until \leq Grade 1: if toxicity related to drug, resume at 1 dose lower; if toxicity not related to drug, resume at same dose or 1 dose lower**.
Grade 4	Discontinue vorinostat. However, if patient is clearly benefiting from treatment, may continue after recovery to \leq Grade 1 at PI's discretion.

*If optimally managed, patients requiring a delay of >2 consecutive weeks will discontinue vorinostat

**Patients requiring a dose reduction to below 100 mg daily of vorinostat at dose level -2 schedule will discontinue vorinostat permanently.

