11.1.3 Analysis of Anti-tumor Activity

This study will aim to obtain preliminary estimates of the anti-tumor activity of the study combination. ORR will be calculated as the proportion of evaluable patients that have confirmed CR or PR, as defined according to the 2014 Lugano Classification, exact 95% confidence intervals will be calculated for these estimates. Response rates will also be evaluated based on number and type of prior therapy(ies). Time to response, duration of response, as well as progression-free survival and overall survival will be estimated using the product-limit method of Kaplan and Meier.

These efficacy analyses will be performed separately for DLBCL, FL, and HL patients. Any patient treated at the RP2D, including those from the dose-escalation cohort, will be included in efficacy analyses. Patients will be evaluable for efficacy assessment if they received at least one dose of vorinostat and one dose of pembrolizumab and underwent at least one response assessment. Patients will be evaluable for efficacy if they discontinued study therapy prior to the first response assessment because of progression of disease rather than solely because of unacceptable toxicity, withdrawal of consent, or investigator decision. If a patient discontinues study treatment prior to the first response assessment due to progressive disease, the treating physician is encouraged to obtain imaging to confirm progression.

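### Sections 7.1.1 and 7.12 end study treatment for any Section 10.2 unacceptable toxicity, while Section 7.6.1.2 and Tables 5 and 7 let treatment go on for some of the same events

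*Combined protocol and SAP*

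**What the plan says.** **The mandatory rule.** Section 7.12 opens its list with "A subject must be discontinued from the trial for any of the following reasons" and includes "Unacceptable adverse experiences, either DLT (Section 7.2) or other unacceptable toxicity (Section 10.2"). Section 7.1.1 uses the same trigger to end study treatment: "unacceptable adverse experiences, either DLT (Section 7.2) or other unacceptable toxicity (section 10.2"). Section 7.12 does attach an exception to the progression item ("A subject may be granted an exception to continue on treatment with confirmed radiographic progression"). The toxicity item has none.

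**The definition it points to.** Section 10.2 covers events at least possibly related to treatment, at any point on therapy. It includes a Grade 3 or higher irAE not back to Grade 1 or lower within 7 days, any other Grade 4 or higher AE, and any Grade 5 AE. It exempts Grade 3 hepatitis below stated laboratory limits, Grade 3 asymptomatic endocrinopathy, local inflammatory response and laboratory abnormalities that are not clinically significant.

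**The rules that keep treatment going.**
- Section 7.6.1.2: "If, according to Table 5, pembrolizumab is discontinued permanently, the patient should continue to receive vorinostat".
- Table 5: pembrolizumab withheld for some irAEs may resume at Grade 0-1 once steroids are tapered. It stops permanently if the event has not resolved within 12 weeks of the last dose.
- Table 7, Grade 4: the default is to stop vorinostat. "However, if patient is clearly benefiting from treatment, may continue after recovery to" Grade 1 or lower, at the PI's discretion.

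**After stopping.** "Subjects who discontinue for reasons other than progressive disease will have post-treatment follow-up for disease status".

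**The concern.** An investigator facing one of these events cannot comply with both sets of rules. Section 16.0 defines a deviation as a divergence from a specific protocol element, so following either section diverges from the other. Two patients with the same event could be managed in opposite ways, each according to the protocol.

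What is at stake is first of all safety and exposure, because the rule chosen decides whether a patient receives more study drug after a serious related toxicity. Toxicity is also the primary endpoint, so time on treatment, and with it the time over which toxicity is observed, would depend on which section was followed. A smaller consequence is for the analysis sets, through the replacement rule in Section 7.4 and the evaluability rule in Section 11.1.3.

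**Working it through.** The plan gives no figure to reproduce. The check takes events that meet the 10.2 definition and reads off what each set of rules instructs. All are assumed at least possibly related and not on the 10.2 exemption list.

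| Event | 10.2 with 7.1.1 and 7.12 | Dose-modification rules |
|---|---|---|
| Grade 3 immune-related diarrhoea/colitis, reaching Grade 1 or lower after 7 days but within 12 weeks of the last dose | Study treatment ends | Table 5: withhold pembrolizumab, may resume after recovery and steroid taper |
| Grade 3-4 pneumonitis or nephritis, not at Grade 1 or lower by 7 days | Study treatment ends | Table 5 stops pembrolizumab; 7.6.1.2 says vorinostat should continue |
| Grade 4 or symptomatic Grade 3 immune-related hypothyroidism, not at Grade 1 or lower by 7 days | Study treatment ends | Table 5: continue pembrolizumab |
| Other Grade 4 or symptomatic Grade 3 immune-related endocrinopathy, not at Grade 1 or lower by 7 days, pembrolizumab withheld | Study treatment ends | Table 5 note: may resume at Grade 2 or lower with hormonal or metabolic control |
| Other clinically significant Grade 4 AE | Study treatment ends | Table 7: vorinostat may continue after recovery, at the PI's discretion |

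Each row gives two different instructions, and no section reconciles them.

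**The two resolution limits.** 12 weeks is 12 × 7 = 84 days, against 7 days in 10.2. Table 5 counts from the last dose, while 10.2 does not say when its 7 days start. If both clocks are assumed to start on the same day, an event resolving in the 84 − 7 = 77 days between the limits falls under both rules.

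**DLTs.** Section 7.12 also names DLTs, whose observation period is 42 days. Section 7.6.1.2 applies Table 5 after that period, and Section 7.7.1 does the same for Tables 6 and 7. Within the period, 7.7.1 forbids vorinostat reductions but permits delays for related toxicity. The overlap for DLTs is therefore narrower.

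**Reach into the analysis sets.** The first response assessment is at cycle 4, day 15-21. With 21-day cycles and no delays that is study day 3 × 21 + 15 = 78 to 3 × 21 + 21 = 84, or day 75 with the 3-day early allowance. Section 7.4 replaces expansion patients who stop study therapy before this assessment for reasons other than progression. Section 11.1.3 makes patients who stop before it evaluable if they stopped "because of progression of disease rather than solely because of unacceptable toxicity, withdrawal of consent, or investigator decision". So the choice of rule can alter replacement or evaluability only for patients stopped before about day 75-84. Section 7.4 does not say whether someone off pembrolizumab but still on vorinostat has stopped study therapy.

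**The case against.** **The rules mostly coexist.** Much of what the tables permit never meets 10.2. Continuing vorinostat after permanent pembrolizumab discontinuation also covers recurrent Grade 2 pneumonitis, exempt Grade 3 hepatitis, Grade 3 nephritis resolved within 7 days, and failure to taper steroids. The 12-week limit also serves Grade 2 events and the taper of at least 4 weeks. Table 7's default for Grade 4 is to stop vorinostat. All of this stands and limits the overlap, but it does not cover the events in the table above.

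**The specific table overrides the general list, or 10.2 serves only the stopping rule in Section 11.2.** No section says either. Sections 7.1.1 and 7.12 cite 10.2 by number as a reason to stop an individual patient. It is true that 11.2 counts the triggering event however the patient is then managed.

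A reader might also infer more than the documents support:
- *That DLTs are equally affected.* They are not, because Tables 5 to 7 are stated to apply after the DLT period. A permitted delay inside it is not explicit permission to resume after a DLT.
- *That patients are lost to the trial.* The opening words of 7.12 say discontinued from the trial, but the same section keeps them in follow-up and 7.1.1 speaks of study treatment. The conflict is about treatment.
- *That patients stopped early for toxicity necessarily leave the ORR denominator.* Section 11.1.3 asks for one dose of each drug and one response assessment, without requiring that assessment to be on treatment. Section 9.5.3.4 provides 12-weekly imaging after stopping for reasons other than progression, so some could still qualify.

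**Conclusion.** The contradiction is real and wrong as written. For a definable group of 10.2 events, Sections 7.1.1 and 7.12 end study treatment without exception, while 7.6.1.2, Table 5 or Table 7 allows at least one drug to continue or resume. Nothing states which prevails.

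Its size cannot be derived from the documents. A reader might apply an assumed toxicity rate to the planned sample: at 10-30%, 52 × 0.10 = 5.2 to 52 × 0.30 = 15.6 patients. That is not supported. The plan states no expected rate of unacceptable toxicity, the 33% in Section 11.2 is a stopping threshold, and only events on which the rules diverge count. Section 4.6.4 also describes 42 patients as already enrolled and 10 more to come. For those 10 the same assumed rates give 1 to 3 patients, again an upper range for the conflict. Nor do the documents support a stated shift in ORR, which would need an event before the first scan and no later assessment.

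The conclusion rests on reading the text as it stands and on the event being at least possibly related and not exempt under 10.2. It matters despite the unknown count because it concerns exposure after serious toxicity.

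**What to change.** - Reconcile Sections 7.1.1 and 7.12 with 7.6.1.2, Table 5, 7.7.1 and Table 7 so that each event meeting 10.2 has one instruction for each drug.
- State which section prevails where they differ. If exceptions to the toxicity item are intended, write them into 7.1.1 and 7.12, as 7.12 already does for progression.
- State how the vorinostat delays permitted in the DLT period relate to the DLT item in 7.12.
- Define three statuses: off one drug, off study treatment, and off trial. Use them consistently in 7.4, 7.12 and 11.1.3, so that replacement and evaluability do not depend on interpretation.
- Record which status applied, and when, for patients already treated who had a 10.2 event.

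Which clinical rule applies is for the sponsor to decide. The cost is a protocol clarification. It needs no new patients or assessments, only a look back at existing treatment records for the last item.
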